Nonetheless NOACs were categorized as a second line treatment due to the restriction of SUKL (local regulatory authority) in Czech Republic and therefore Czech patients are primarily treated with warfarin (including patient post stroke/TIA) and NOACs treatment can be initiated only in case of defined contraindication. Czech Cardiology Society, Society of Ambulatory Specialist together with main Czech Public Insurance House (VZP) defined number of conditions where safe and efficacious anticoagulation therapy by VKA cannot be adequately ensured. Prescription of NOACs as first line therapy is allowed in these defined situations . One of the situations is described as higher sensitivity to warfarin. There are two variants of two genes, CYP2C9 and VKORC1, account for 30-50% of the variability in dosing of warfarin. The prevalence of CYP2C9 (allele \*1, \*2 and \*3) and VKORC1 (-1639 G and A alleles), and their combinations in Czech population was analyzed and about 30% of the Czech healthy subjects have genetically determined higher sensitivity to warfarin. Individuals with higher sensitivity to warfarin are eligible for first line NOACs treatment in secondary prevention of stroke.

Additionally there is no healthcare resource use (hospitalization days, outpatient visits, and clinical events) comparison of apixaban to warfarin available in the Czech Republic. The most intensive resource use is expected in the first 6 months after stroke, especially because of a high risk of the event recurrence. Considering that there are less outpatient visits, less monitoring needed and lower risk of the complications and adverse events expected with apixaban. Real-world data about the impact of different treatment strategies on healthcare resource use and costs are essential arguments for establishing the clinical value of new therapies.

In the light of this situation we have designed this study to compare the healthcare resource use in patients who use warfarin or apixaban in secondary stroke prevention as a first line therapy.

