## 7. RESEARCH QUESTION AND OBJECTIVES

The primary objective of the study is:

- Description of direct costs related to warfarin/apixaban treatment during the first 6 months of the secondary stroke prevention in NVAF patients.

The secondary objectives of this study are:

- Comparison of direct costs related to warfarin/apixaban treatment during the first 6 months of the secondary stroke prevention in NVAF patients;
- Number of hospitalization days in the first 6 months of the treatment;
- Number of ischemic/hemorrhagic strokes in the first 6 months of the treatment;
- Number of ischemic events in the first 6 months of the treatment;
- Number of major/minor hemorrhagic events in the first 6 months of the treatment;
- Mortality rates in both cohorts;
- Number and costs of medical procedures directly related to the treatment in the first 6 months (visits, hospitalizations, labs, diagnostics, etc.);
- Overall safety (adverse events) of the treatment.

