## 8. RESEARCH METHODS

### 8.1. Study design

This is a double arm, non-interventional, single-center retrospective study according to Czech legal definitions (Law 378/2007 Sb.). For the description of the direct costs related to warfarin/apixaban treatment, retrospective data will be used for both, the warfarin treatment arm and the apixaban treatment arm.

The study follows two cohorts of NVAF patients, who used either warfarin or apixaban as a secondary stroke/TIA prevention.

The data to be collected retrospectively:

- Consecutive data of the 6 months after the first prescription of warfarin/apixaban (indicated as a secondary stroke/TIA prevention).

Considering the retrospective design of data collection, the non-interventional study will not impose any additional procedures, assessments or changes to the routine management of subjects. Data for the study will be obtained from clinical practice records and transcribed to an anonymous electronic case report form (e-CRF).

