### 8.2.1. Inclusion criteria

The data will be collected for patients who have met all of the following inclusion criteria:

1. Diagnosis of non-valvular atrial fibrillation (NVAF);
2. New initiation of anticoagulation therapy (apixaban or warfarin) due to the ischemic event (stroke/TIA) meaning patients previously not anticoagulated due to diagnosis of NVAF;
3. Indication to anticoagulation therapy as a secondary stroke prevention within 7 to 30 days after the stroke/TIA event;
4. Apixaban arm: genetically determined higher sensitivity to warfarin;
5. Patients whose status allowed oral treatment with apixaban/warfarin;
6. Age  $\geq 18$ ;
7. Access to patient's records of the first 6 months of the warfarin/apixaban treatment.

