### 8.3. Variables

**Table 1:** Table of variables

Variable	Role	Data source(s)	Operational definition
Age, Sex, BMI, date of index event (stroke/TIA diagnosis), date of indication to warfarin/apixaban treatment (index date)	Demographic data	Medical records	Specified in e-CRF
CHA2-DS2-Vasc score, HAS-BLED score	Outcome	Medical records	Specified in e-CRF
Therapy after index event, prior to warfarin/apixaban treatment	Exposure	Medical records	Specified in e-CRF
Warfarin/apixaban therapy information (dosage; number of INR measurements in warfarin arm)	Exposure	Medical records	Specified in e-CRF
Number and type of resource use during the first 6 months of warfarin/apixaban treatment (outpatient visits, diagnostic procedures, labs, medication, hospital admissions)	Outcome	Medical records	Specified in e-CRF
Amount, type, severity and cost of ischemic events	Outcome	Medical records	Specified in e-CRF

Amount, type, severity and cost of major/minor hemorrhagic events	Outcome	Medical records	Specified in e-CRF
Adverse events	Outcome	Medical records	Specified in e-CRF

*Index date = The index date will be the first date of OAC prescription indicated for secondary stroke/TIA prevention.*

*Index event = The index event will be the first stroke/TIA event based on which the OAC treatment will be initiated.*

*Index event date = The index event date will be the date of first stroke/TIA event based on which the OAC treatment will be initiated*

*Therapy after index event, prior to warfarin/apixaban treatment (Aspirin, clopidigrel, Trombolytics (rhu-tPA - alteplase, urokinase), Anticoagulants (heparin, heparinoids), other)*

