### **8.7. Data analysis**

The statistical analyses will be descriptive and exploratory. Given the nature of the study, which is exploratory, it is not designed to confirm or reject predetermined hypotheses.

Categorical outcomes will be summarized by the number and percentage in each category. Continuous outcomes will be summarized by mean, standard deviation, median, minimum and maximum values.

All analyses will be based on the full analysis set, comprising all subjects enrolled into the study.

The paired tests will be applied in the detailed analyses. Relevant endpoints will be compared using the differences in mean / median or proportion. Statistical significance will be assessed at a significance level of 0.05. All statistical analyses will be conducted using STATA version 13.1.

**Table 2:** Table of descriptive analyses

Variable	Categorical outcome	Continuous outcome
Age		X
Sex	X	
Body height, weight, BMI		X
Period between stroke/TIA and start of secondary stroke prevention (duration in days)		X
Period between stroke/TIA and start of secondary stroke prevention (medication)	X	
CHA2-DS2-VASc Score		X
Stratification: (0, 1, 2-9)	X	
HAS-BLED Score		X
Stratification: (0-2, 3-9)	X	
Warfarin/apixaban dosage		X
INR measurements	X	
Number and type of outpatient visits, diagnostic procedures, labs, hospital admissions	X	
Cost of outpatient visits, diagnostic procedures, labs, medication, hospital admissions		X
Amount, type and severity of ischemic events	X	
Cost of ischemic events		X
Amount, type, severity of major/minor hemorrhagic events	X	

Cost of major/minor hemorrhagic events		X
Adverse events	X	

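### The delay from stroke/TIA to first prescription (7 to 30 days) is recorded and described but not used when costs, hospital days and ischemic events are compared between arms

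*Combined protocol and SAP*

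**What the plan says.** Section 8.1 defines the data to be collected as "Consecutive data of the 6 months after the first prescription of warfarin/apixaban (indicated as a secondary stroke/TIA prevention". Table 1 in section 8.3 fixes the start: "The index date will be the first date of OAC prescription indicated for secondary stroke/TIA prevention". Inclusion criterion 3 (section 8.2.1) sets when this may happen: "Indication to anticoagulation therapy as a secondary stroke prevention within 7 to 30 days after the stroke/TIA event". Criterion 4 applies to one arm only: "Apixaban arm: genetically determined higher sensitivity to warfarin".

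On timing, section 6 states: "The most intensive resource use is expected in the first 6 months after stroke, especially because of a high risk of the event recurrence". Section 7 makes a between-arm analysis a secondary objective: "Comparison of direct costs related to warfarin/apixaban treatment during the first 6 months of the secondary stroke prevention in NVAF patients". It also lists hospitalization days and ischemic events over the first 6 months of treatment.

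Table 1 collects both the index event date and the index date. Table 2 (section 8.7) summarises the interval in days and the medication given during it. For the comparison itself, section 8.7 says: "Relevant endpoints will be compared using the differences in mean / median or proportion". It adds "The paired tests will be applied in the detailed analyses", but defines no pairs. It names no covariate, stratification or weighting, and section 8.9 does not list a differing delay as a limitation.

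**The concern.** Patients enter the cost window at different points after the stroke/TIA. By the plan's own premise, resource use is heaviest in the first 6 months after stroke, so a later start exchanges some of those days for days beyond them. If one arm starts later on average, part of any crude difference reflects where its window sits and not the drug.

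There is a reason to think the delays might differ: the apixaban arm requires a genotype result and the warfarin arm has no such entry condition. The comparisons at stake are cost, hospital days and ischemic events. The primary objective, a description of cost within each arm, is not affected in the same way, because starting at the prescription fits the question of what the first 6 months of treatment cost.

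**Working it through.** The plan gives no power calculation, cost profile or delay by arm, so there is no stated figure to reproduce. The check asks how large the artefact could be with no drug effect.

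**Inputs from the documents.** Window of 6 months, taken as W = 182.5 days; start between day 7 and day 30; 120 patients per arm; significance level 0.05 (two-sided assumed).

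**Position of the window.** A day-7 start covers 182.5 − 7 = 175.5 days of the first 6 months after stroke plus 7 later days. A day-30 start covers 152.5 plus 30. The largest possible shift is 23 days, or 23/182.5 = 12.6% of the window.

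**Two-phase reading of section 6.** Let daily cost be q during the first 182.5 days after stroke and 1 afterwards (q is assumed). A start on day s costs q(W − s) + s. This is linear in s, so only the mean delay matters. Starting d days later lowers total cost by the fraction d(q − 1) / [q(W − s) + s], with limit d/(W − s) if nothing is spent after 6 months.

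| Mean start, earlier vs later | q = 2 | Limit |
|---|---|---|
| Day 14 vs 17 | 3/351 = 0.9% | 3/168.5 = 1.8% |
| Day 14 vs 21 | 7/351 = 2.0% | 7/168.5 = 4.2% |
| Day 7 vs 30 (extreme) | 23/358 = 6.4% | 23/175.5 = 13.1% |

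**Steeper decline (assumed, not in the documents).** Let the daily rate be 1 + (R − 1)·2^(−t/H), with t in days since stroke. The window cost is W + (R − 1)·(H/ln 2)·[2^(−s/H) − 2^(−(s+W)/H)]. For R = 5 and H = 30 days, a day-14 start costs 305.9 and a day-21 start 287.5, a gap of 6.0%. Over R from 2 to 20 and H from 7 to 60 days, the gap is:
- 0.4% to 7.1% for day 17 vs 14;
- 0.7% to 15.0% for day 21 vs 14;
- 2.4% to 40.6% for day 30 vs 7.

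**Zero cases.** With equal delays, or a flat cost profile (q = 1 or R = 1), the gap is 0%.

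**Effect on the test.** Take an unpaired comparison of means and a coefficient of variation CV (assumed). A spurious relative gap b shifts the test statistic by b / [CV·√(2/120)], where √(2/120) = 0.129. With CV = 1, a 3% gap raises rejection from 5% to 5.6% and a 5% gap to 6.7%. With CV = 0.5 the figures are 7.5% and 12.1%. A 10% gap, which needs a steep decline or an extreme delay difference, gives 12.1% at CV = 1 and 34.1% at CV = 0.5.

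**The case against.** The case against is substantial, and most of it stands as a limit on the claim.

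- **The delay is not ignored.** It is collected and tabulated in a study declared descriptive and exploratory, so an imbalance could be seen. But seeing it in a table does not remove it from the cost difference.
- **Section 6 gives no gradient within the first 6 months.** It contrasts that period with what follows. Even a day-30 start still covers 152.5 of those 182.5 days. Any steeper early decline is the reader's assumption.
- **No difference in delay is shown.** Both arms share the 7-day minimum, and section 8.2 requires a center that can itself determine warfarin sensitivity, so results may be available before day 7. Warfarin patients may also have been tested, and waited, before the choice of drug.
- **The direction depends on all else being equal.** If sicker patients start later, the later arm could look dearer. No variable for index-event severity is listed.
- **The cost objective concerns costs related to treatment.** Drug and laboratory costs need not fall with time since stroke, and the plan does not say whether general post-stroke care counts. Hospital days and ischemic events, however, are listed in section 7 without that limit.

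A reader might infer that the design favours apixaban because its patients wait for a genotype result. The documents do not support this: they give no turnaround time and do not say that the result delays prescribing. A reader might also quote the gap of about 41%. That needs every patient in one arm to start on day 7, every patient in the other on day 30, and a very steep assumed decline.

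**Conclusion.** The point holds in a limited form. The window start varies by up to 23 days relative to the stroke/TIA, the delay is known for each patient, and the planned comparison does not use it. Under the two-phase reading of section 6, a mean difference of 3 to 7 days makes the later arm look about 1% to 4% cheaper with no drug effect. Larger figures rest on assumed steep declines in cost.

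All of this is conditional on the delays differing between arms, on other factors being equal, and on early post-stroke care entering the counted costs. Anchoring the window at first prescription is not an error. The gap is that a baseline value already in hand is left out of the comparison.

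**What to change.** In section 8.7, state that the warfarin–apixaban comparisons of cost, hospital days and ischemic events are adjusted for days from index event to index date, entered as a continuous covariate. Enter it alongside the other baseline variables already collected: age, sex, BMI, CHA2DS2-VASc, HAS-BLED and the therapy given before the anticoagulant. Report the delay by arm. The sentence on paired tests needs to be reconciled with this, since no pairs are defined.

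Keep the 6-month window from first prescription. A common post-event window (about day 30 to day 189) may look attractive but is better left out. It would remove up to 23 days of early treatment from early starters only, depart from the objective of the first 6 months of treatment, and need service dates that the documents do not show. A continuous term is also preferable to delay bands: three bands would leave about 120/3 = 40 patients per arm in each.

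The cost is a sentence or two in section 8.7 and a little more analysis, with no new data. Adjustment does not deal with unrecorded factors such as index-event severity, so confounding from those remains and should be stated in section 8.9.

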## 8.2. Setting

In total, this non-interventional study follows the population of 240 patients with nonvalvular atrial fibrillation. From 240 NVAF patients, 120 patients are treated with warfarin and 120 patients are treated with apixaban.

The study will follow the period of 6 months after the prescription of warfarin or apixaban for the secondary stroke/TIA prevention.

The data will be collected retrospectively from clinical practice hospital records.

It's expected that the data will be collected within 3 months from the start of the study – the data collection will be closed as soon as there are 120 patients enrolled in each study arm. If there are not 120 patients enrolled in each study arm after 3 months of the data collection, the period can be prolonged up to 6 months from the start of the study.

Requirements for the center's eligibility are as followed: center able to genetically determine patients' higher sensitivity to warfarin; neurologists, who work in cerebrovascular center in a hospital; satisfactory experience in the care of patients with NVAF and treatment with warfarin and NOAC; sufficient number of patients with NVAF diagnosis fulfilling eligibility criteria.

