#### **8.5. Study size**

The study will be descriptive in nature. No sample size was statistically determined. Based on experience of experts on anticoagulant treatment the data from 120 patients per study arm can be collected.

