#### **8.6. Data management**

The data will be transcribed by the physician to an anonymous electronic Case Report Form from the patient's medical records. The data will be obtained retrospectively and no patient data identification will be possible.

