## 8.9. Strengths and limitations of the research methods

The study design is considered to be the main strength of this study. It brings a unique opportunity to compare the outcomes of two cohorts of patients fulfilling the same inclusion criteria. Another strength of the design is data collection in real-world setting without any patient's selection according subgroups characteristics. The main limitation of the research may be a random distribution of patients on warfarin/apixaban treatment.

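### Section 8.2 fills each arm to 120 charts with no order of entry, no earliest index date and no log of eligible charts left out, so selection on known outcomes is not prevented

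*Combined protocol and SAP*

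**What the plan says.** Section 8.2 fixes the composition of the study: "From 240 NVAF patients, 120 patients are treated with warfarin and 120 patients are treated with apixaban". Entry stops by quota: "the data collection will be closed as soon as there are 120 patients enrolled in each study arm". If the quota is not met in 3 months, collection may run to 6 months.

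Section 8.5 explains the number. "No sample size was statistically determined", and "Based on experience of experts on anticoagulant treatment the data from 120 patients per study arm can be collected".

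The study is retrospective and single-center (section 8.1). Criterion 7 in section 8.2.1 admits only patients whose records for the first 6 months of treatment are accessible. Section 8.6 says who handles the charts: "The data will be transcribed by the physician to an anonymous electronic Case Report Form". Section 8.3 defines the index date as the first relevant anticoagulant prescription and gives no calendar limits for it. The full analysis set in section 8.7 consists of the enrolled subjects only.

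Section 8.9 counts as a strength that there is no selection of patients by subgroup characteristics.

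**The concern.** In a retrospective chart study the sampling rule does the work that prospective enrollment does elsewhere. Here the costs, strokes, bleeds and deaths of the 6 months have already happened, and they are in the same record from which eligibility is judged. If more than 120 charts in an arm qualify, something decides which 120 are used, and the plan does not say what.

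Two things are at stake. First, if charts with events are more or less likely to be entered than charts without, the primary cost description is distorted. So are the event counts, the mortality rates and the between-arm cost comparison listed as secondary objectives in section 7. Second, without a common index-date window the two arms can come from different periods, and changes in practice over time would then be mixed with the drug comparison. Because eligible charts left out are not recorded, a reader of the results could neither detect nor rule out either problem.

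**Working it through.** **The plan's own figure.** 120 + 120 = 240, which agrees with section 8.2. There is no sample-size formula to reproduce, because section 8.5 says the number was not derived statistically.

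**Does any other text supply a sampling rule?**
- Section 8.1 uses the word consecutive: "Consecutive data of the 6 months after the first prescription of warfarin/apixaban". It describes each patient's follow-up data, not the order in which patients are taken.
- Section 5 (July to September 2020) and the 3-to-6-month period in section 8.2 date the data collection, not the index prescriptions. With criterion 7 they imply a latest index date: 6 months before the end of September 2020 is about the end of March 2020. Nothing implies an earliest one.
- The criteria in 8.2.1 and 8.2.2 decide who is eligible, not which eligible charts are entered.
- No section mentions a screening log or a patient list drawn up without sight of outcomes.

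**Size of a possible bias.** The following are assumptions, not figures from the documents: N eligible charts in an arm, of which E = 0.10 × N have an event, and a relative chance w that an event chart is picked at each draw, with w = 0.5 or 2. Drawing 120 charts without replacement gives a Wallenius noncentral hypergeometric count. Its mean m is closely approximated by the solution of

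1 − m/E = [1 − (120 − m)/(N − E)]^w

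Example with N = 200, E = 20:
- w = 0.5: m = 7.73. Left side 1 − 7.73/20 = 0.613; right side (1 − 112.27/180)^0.5 = 0.376^0.5 = 0.613. Observed rate 7.73/120 = 6.4%.
- w = 2: m = 16.4. Left side 1 − 16.4/20 = 0.180; right side (1 − 103.6/180)^2 = 0.424^2 = 0.180. Observed rate 16.4/120 = 13.7%.

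Exact means for a range of N:

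| Eligible charts N | Event charts E | Observed, w = 0.5 | Observed, w = 2 |
|---|---|---|---|
| 120 | 12 | 10.0% | 10.0% |
| 130 | 13 | 8.2% | 10.8% |
| 150 | 15 | 7.3% | 11.9% |
| 200 | 20 | 6.4% | 13.7% |
| 300 | 30 | 5.9% | 15.3% |

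The true rate is 10% in every row. The bias is zero when all eligible charts are entered and grows as the share entered falls.

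**Could the arms cover different periods?** Section 6 says about 30% of healthy Czech subjects are genetically more sensitive to warfarin. Assume, for illustration only, that this share applies at the center and that genotype alone decides the drug. Then 120 apixaban patients need 120/0.30 = 400 new starters, which leaves 400 − 120 = 280 on warfarin. Of these, 120/280 = 43% would be entered. Taken in date order, the warfarin quota fills after 120/0.70 ≈ 172 starters and the apixaban quota after 400. For sensitive shares of 20% and 40%:
- 20%: 600 starters, 480 on warfarin, 25% of them entered, warfarin quota full after 150.
- 40%: 300 starters, 180 on warfarin, 67% of them entered, warfarin quota full after 200.

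Under these assumptions the arms would span different periods even without any deliberate choice of charts.

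**The case against.** The strongest reply is that the plan is silent rather than wrong. It says the physician transcribes the data; it does not say that the physician picks patients at will. Section 8.2.1 can be read as taking eligible patients as they are found until the quota is met. The pool may also be close to 120 in at least one arm: section 8.5 says only that 120 per arm can be collected, section 8.2 plans for a shortfall, and the apixaban arm needs a genetic result. With 130 charts the distortion is small, and with 120 there is none. The study is also declared descriptive and exploratory.

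Most of this stands, and it limits the point to an opportunity for bias of unknown size. It does not remove the point. A description depends on its sample, section 8.7 adds tests ("Statistical significance will be assessed at a significance level of 0.05"), and only a log could show that the pool was near 120.

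A reader might infer four stronger points, none of which the documents support:
- *Section 8.9 contradicts the quota.* The sentence beginning "Another strength of the design is data collection in real-world setting without any" goes on to limit itself to selection by subgroup characteristics. It makes no claim about outcomes or order of entry.
- *Collecting more patients could not help.* Entering more of the same pool reduces the bias, to zero when all are entered.
- *The arms would differ about twofold with no true difference.* The ratio 13.7/6.4 = 2.1 needs 200 eligible charts in both arms and opposite twofold preferences. With 150 the ratio is 11.9/7.3 = 1.6, and with 130 it is 10.8/8.2 = 1.3.
- *Price changes over time would bias the costs.* The documents do not say how resources are priced; with one tariff for all patients there would be no such drift.

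**Conclusion.** The concern holds in a limited form. The quota is the only sampling rule, outcomes are in the chart at entry, and no section sets an order of entry, an earliest index date or a record of eligible charts left out. Following the plan as written therefore permits outcome-dependent selection and arms from different periods. Nothing in the documents shows that either will happen.

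How much it matters turns on the unknown number of eligible charts. Under the assumed 10% event rate and twofold preference, it ranges from no effect at 120 charts to observed rates of 5.9% or 15.3% at 300. The event rate, the preference and the pool sizes are all assumptions. The calendar illustration further assumes that the 30% population figure carries over to this center. The change is worth making because it is cheap and settles the question whatever the pool turns out to be.

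**What to change.** In section 8.2:
1. List all patients meeting 8.2.1 and 8.2.2 from the hospital records, without reference to outcomes.
2. State one index-date window common to both arms, ending at least 6 months before extraction.
3. Enter all listed patients. If an arm exceeds 120, take a random or systematic sample spread across the whole window. Consecutive entry up to 120 is not enough, because the larger arm would fill from a shorter period.
4. Keep a log of eligible, entered and skipped charts with reasons, and report it by arm.

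In section 8.9, make clear that the stated strength concerns subgroup characteristics only, and refer to the sampling procedure in 8.2.

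The cost is about a paragraph of protocol text plus a modest listing and logging effort at one site, with no patient contact. The rarer arm may end below 120. That is tolerable, because 120 was a feasibility figure and no power calculation depends on it.
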